Interested participants will fill out a brief questionnaire to confirm eligibility either online or over the phone with research staff. Participants will be asked a series of questions regarding their tobacco product usage, health status, willingness to travel to Columbus for study visits, and brief demographic and contact information. Research staff will review the screener questionnaire for eligibility and inform participants if they are eligible for this study or not. Research staff will provide a study overview, discuss study procedures, and ascertain participant interest. Should the participant wish to proceed, research staff will schedule the first visit and communicate IRB-approved guidance, such as the CTR address and the need for subjects to abstain from tobacco products for 12 hours prior to the study visit. Participants will be advised that each research visit must be scheduled 2 or more days apart and that they must bring their own brand of cigarettes to the study visits in case they are randomized to smoke cigarettes at a particular visit.

Clinic Visits

Aim 1: Participants will be invited to the CTR to complete study procedures. At visit 1, informed consent will be collected. During visits 1-3, participants will complete an exhaled CO test, take a pregnancy test if applicable, a line will be placed for IV blood draw by the staff research nurse for IV blood draws throughout the course of the study visit, and be asked to either smoke their usual brand or insert a 3mg or 6mg NP and then sit in the room for 60 minutes. At each visit, participants will be randomly assigned to use 3mg Wintergreen pouches, 6mg Wintergreen pouches or their own brand of cigarettes. Participants will be asked a series of 3 questionnaires before, during, and after each product is used. Blood draws will be collected from the line at 0 5, 15, 30, 60, and 90-minutes. 3mLs, or a little less than 1 teaspoon, of blood will be drawn at each timepoint.

Measures of craving and withdrawal relief will be assessed at each blood draw (see attached surveys). If a collection interval is not met there will be no draw retroactively. Participants will be assessed for AE throughout procedures and prior to leaving the visit.

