Participants will need to abstain from tobacco and nicotine products for ≥ 12 hours prior to their study visit. To check for abstinence from tobacco, participants will perform exhaled carbon monoxide testing ($eCO < 10\text{ppm}$) and confirm via self-report that they have not used any other nicotine products over the last 12 hours.

Pregnancy Test

All subjects capable of becoming pregnant will need to take and produce a negative pregnancy test in order to proceed further.

Pre-intervention questionnaire to be administered

This questionnaire will assess sociodemographics, tobacco use history, NP use history, and nicotine dependence. These questionnaires will be administered during Visit 1.

IV line insertion

Because blood draws will occur at set intervals, an IV line will be inserted by a trained staff nurse.

Blood draw to obtain baseline plasma nicotine levels

Next, participants will be reminded that in addition to the exhaled CO test, their abstinence will be confirmed at the time of visit via blood plasma nicotine analysis. 3 mL venous blood sample will be collected for later analysis to confirm abstinence. This blood draw will also be used to establish baseline plasma nicotine levels to estimate total nicotine delivery.

Administer intervention

Aim 1: The participant will receive a 3mg NP, 6mg NP, or be asked to smoke one cigarette of their usual brand depending on the randomization assignment. If smoking a cigarette, participants will be asked to smoke one cigarette following a standardized puffing protocol: they will take one puff every 30 seconds for 5 minutes. If using an NP, participants will be asked to place the pouch between their upper lip and gum and leave it in place for 30 minutes.

Aim 2: The participant will receive a 3mg tobacco-derived NP or a 3mg synthetic NP on randomization assignment. Participants will be asked to place the pouch between their upper lip and gum and leave it in place for 30 minutes.

Peri-intervention questionnaire to be administered

The QSU and MNWS surveys will be administered while at each blood draw interval of 0, 5, 15, 30, 60, and 90 minutes.

Post-intervention questionnaire to be administered

Measures of product appeal and behavioral intentions will be assessed after the participant has the cigarette or NP (Aim 1) or the tobacco-derived vs. synthetic NP (Aim 2).

Schedule return visit and provide gift card for participation

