Schedule return visit per subject and interviewer availability that is >2 days after the current visit. Provide \$100 via Clincard for their participation out of the up to \$350 possible. If it is their last visit has been completed within 1 month from consent, they will receive \$150 during their last visit.

Post-Enrollment Survey

6 months after enrolling, participants from Aims 1 and 2 will be recontacted via phone, text, and email for the opportunity to participate in a short online REDCap survey. Participants will complete a short consent addendum and respond to survey questions regarding their current tobacco product use and opinions surrounding nicotine pouches. For their time, they will receive a \$10 Amazon gift code.

Procedure Manual

Study procedures, including conducting pregnancy tests, blood draws, blood processing and analysis, gift card administration, and other procedures will be thoroughly explained in the study procedure manual.

4. Study Administration

Randomization, Blinding, and Unblinding

Participants will be randomized within the secure database, REDCap. The randomization piece involves at which of the 3 visits they are to use each product (Aim 1: 3mg NP, 6mg NP, or their own usual brand cigarette and Aim 2: the tobacco-derived 3mg tobacco-derived NP or the 3mg synthetic pouches). Participants will be blinded during study visits and at the end of their third visit will be informed which product they had at each visit.

Study Timelines, Number of Sites, and Enrollment

Participant Timeline

There will be a total of 3 study visits and 1 online survey opportunity 6 months after the completion of the final study visit. The study timeline for each participant will vary. Clinic visits can be completed in as little as a week and a half or as long as 2 months, but will ideally be completed within 3 week's timeframe for retention and administrative purposes. The study visits will take approximately 3 hours each. The online survey will take approximately 10 minutes to complete and will be offered 6 months after completing the final visit.

Duration of Study

We anticipate the clinical trial to take six months to complete. After that, we anticipate that it will take 1-1.5 years to clean and analyze data and disseminate results.

Total Number of Study Sites

All recruitment and enrollment activities will be completed within the CTR.

Total Number of Subjects Projected

55 subjects will be enrolled and each subject must meet I/E criteria.

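### The plan says participants are blinded without qualification, but in Aim 1 they cannot be blinded to smoking their own cigarette, so the cigarette-versus-pouch self-report contrasts are open-label

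*Combined protocol and SAP*

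**What the plan says.** Section 4, under Randomization, Blinding, and Unblinding, describes what is randomized. For the first aim it lists the products as "Aim 1: 3mg NP, 6mg NP, or their own usual brand cigarette". The sentence that follows the list reads: "Participants will be blinded during study visits and at the end of their third visit will be informed which product they had" at each visit. No aim, product or comparison is excepted.

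Other sections describe how the products are supplied and used:

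- Screening and scheduling phase: participants are told that "they must bring their own brand of cigarettes to the study visits in case they are randomized to smoke cigarettes at a particular visit".
- Section 3, Administer intervention, cigarette visit: "they will take one puff every 30 seconds for 5 minutes".
- Section 3, Administer intervention, pouch visit: "participants will be asked to place the pouch between their upper lip and gum and leave it in place for 30 minutes".

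Section 3 also schedules the self-report. The QSU and MNWS are given at 0, 5, 15, 30, 60 and 90 minutes. Product appeal and behavioral intentions are assessed after the product, and the cigarette is named as one of the products in Aim 1. Statistical Considerations tests the main effect of product on plasma nicotine, subjective effects and intentions, and does not mention blinding.

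**The concern.** The blinding sentence claims a property that the design cannot have for one of the three Aim 1 products. Craving, withdrawal and appeal are the participant's own judgements, and these can move with what the person expects of a product. Aim 1 enrolls daily smokers and excludes anyone who used a pouch in the past 3 months. The cigarette visit therefore sets a familiar product against one with no recent use, and the participant knows which is which.

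The wording at issue governs how the results are read. If the sentence carries over into a report, a reader would credit the cigarette-versus-pouch ratings with a protection that they do not have. The analysis section contains nothing that would prompt the correction.

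**Working it through.** No arithmetic beyond a count is needed. The check sets the sections against each other.

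**1. Can the cigarette be masked?** The participant supplies it, it is their usual brand, and it is smoked in timed puffs over 5 minutes. A pouch is held under the lip for 30 minutes. The documents describe no dummy or double-dummy procedure. A separate procedure manual is mentioned but not included. It might say how pouches are masked, but it could not hide a person's own cigarette from that person.

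**2. How many comparisons are affected?** Three products give 3 × 2 / 2 = 3 pairs.

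| Aim 1 pair | Participant blinding |
|---|---|
| Cigarette vs 3mg pouch | Impossible |
| Cigarette vs 6mg pouch | Impossible |
| 6mg pouch vs 3mg pouch | Possible, if the pouches are masked |

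That is 2 of 3. In Aim 2 all three products are pouches, so this argument rules out none of its 3 pairs.

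**3. Which outcomes are exposed?**

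| Outcome | Exposed in cigarette-versus-pouch contrasts? |
|---|---|
| Plasma nicotine | Much less; it is a laboratory assay |
| QSU, MNWS | Yes; self-reported at every blood draw |
| Product appeal | Yes; assessed after the cigarette as well as after a pouch |
| Intentions | Only for items asked in the cigarette condition; the surveys are not in the documents |

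**4. Does the plan use these contrasts?** Yes.

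- The Background closes by naming subjective as well as pharmacokinetic results against cigarettes as what Aim 1 is to establish.
- The Aim 1 primary objective is abuse liability relative to cigarette smoking. Exploratory objectives measure it by subjective effects and by intentions.
- The planned models test product on all three outcome families.

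**5. Which stated hypotheses depend on them?** Neither. Under Description and Rationale of Intervention, hypothesis 1a (pouches against the cigarette) concerns how much nicotine is delivered and how fast. Hypothesis 1b, the only Aim 1 hypothesis on appeal and intentions, compares the two pouch strengths. The power statement uses total nicotine delivery and maximum concentration only.

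**The case against.** The strongest reply is that nobody would be misled. The protocol says openly that participants bring and smoke their own brand, and the hypotheses already place cigarette-versus-pouch inference on plasma nicotine and the appeal hypothesis on pouch against pouch. Much of this stands. It means that the problem is one of wording and interpretation and leaves the powered comparisons alone. It does not remove the problem, because the objectives and the models reach beyond the two hypotheses, and no section qualifies the blinding sentence.

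A second reply is that knowing the product is part of what is being measured. The Background counts consumer perception among the components of appeal, so familiarity with one's own brand belongs partly to the comparison. This also stands. A reader might infer that the difference in ratings is contaminated by pure bias, but the documents do not support that. The accurate description is an inherently open-label comparison that includes familiarity and expectation.

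Three other stronger readings are tempting:

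- *Every subjective and intention outcome is affected.* The intentions described concern using and switching to pouches, and the items cannot be seen. Whether each has a cigarette-versus-pouch contrast cannot be verified.
- *The pouch comparisons are blinded.* The documents do not establish this. Aim 1 uses wintergreen pouches at both strengths and Aim 2 uses wintergreen for all three brands. However, no masking method is described, and nothing says whether staff know the assignment.
- *The trial will be misreported.* The documents contain no reporting text that calls these ratings blinded. The risk comes from the unqualified sentence and has not occurred in the documents.

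**Conclusion.** The point holds in a limited form. The blinding statement is wrong as written for Aim 1: participant blinding is impossible in 2 of the 3 product pairs. The consequence falls on self-report collected in the cigarette condition, namely QSU, MNWS, appeal, and whatever intention items are asked there. The size of any expectation effect cannot be derived from the documents, and none is claimed.

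A reader might conclude that the main Aim 1 findings are compromised. The documents do not support that. Plasma nicotine under hypothesis 1a is little exposed, and hypothesis 1b compares two pouches. Nor is the open-label cigarette a design error, since it is inherent in using a usual-brand reference. The fault lies in the unqualified claim and in the silence of the analysis section.

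The conclusion assumes only that a person smoking a cigarette they brought knows that they are doing so. It does not assume that the pouches are, or are not, successfully masked.

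**What to change.** In the blinding section, limit the statement to comparisons among pouches: strength in Aim 1, brand and nicotine source in Aim 2. Make it only to the extent that masking is actually done. Possible wording: *In Aim 1 the cigarette condition is open-label. At pouch visits, participants are masked to pouch strength (Aim 1) or to brand and nicotine source (Aim 2) by [method]; [roles] know the assignment.* If there is no masking method, say that the pouch comparisons are open-label too. Apply the same limit to the disclosure after the third visit.

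In Statistical Considerations, add that cigarette-versus-pouch contrasts on self-reported outcomes are open-label and will be reported and interpreted as including product familiarity and expectation. They can still be estimated and tested as planned. List which intention items are asked after the cigarette, so that the reach of the label is clear.

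The cost is a slightly less favourable blinding claim and a few sentences of text. Procedures, assays, models and sample size do not change.

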Data Collection and Management

Data will be collected and stored electronically in the secure database, REDCap. Data will only be accessible to approved study personnel and will be secured through multiple firewalls. Subjects' first and last names will be deidentified and not linked with the data. The consent forms with first and last names will be databased electronically in REDCap but will not be downloaded with any study data.

Subject Completion, Withdrawal, and Early Termination

Participants will be invited to complete 3 study visits (i.e., participants cannot participate in both Aim 1 and Aim 2) and a supplemental, online survey opportunity to be completed once 6 months after the third clinic visit. The participant timeline will be complete once the 3 study visits are complete. Participants have the option to withdraw at any point by expressing their desire to withdraw to study staff orally or in writing. Study staff will complete a Withdrawal form to document this event. If at any point a participant becomes unable to complete study tasks per protocol (e.g., repeated violations of nicotine abstinence; inconsistent responses reported on questionnaires; showing up to a clinic visit impaired; injury, illness, or medications that impair ability to accurately complete study measures; or inappropriate behavior toward study staff), [name] reserves the right to ET a participant.

Informed Consent Process

Informed consent will be collected in person by a trained study staff member at the beginning of the initial study visit. Signatures will be documented electronically in REDCap and subjects will be offered an email or printed copy of the consent for their records.

For the 6-month follow on survey, an online consent addendum will be completed prior to the online survey. Signatures will not be collected for the consent addendum and instead the online framework of clicking "next page" will suffice.

Payment to Subjects

Participant compensation will be administered in two tiers: clinic visits and completion bonus.

Aim 1: For each clinic visit, subjects will receive \$150. If participants complete all three visits within a month, they will receive a \$50 bonus for their participation. Participants could earn up to \$500 for their participation. Compensation will be offered in the form of Clincard.

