Aim 2: For each clinic visit, subjects will receive \$100. If participants complete all three visits within a month, they will receive a \$50 bonus for their participation. Participants could earn up to \$350 for their participation. Compensation will be offered in the form of Clincard.

If any part of the visit is not possible to complete, participants will be given \$50 to thank them for their time.

Aims 1 & 2: 6 months after the final visit is complete, participants from Aim 1 and 2 will be offered participation in a short, 10-minute online survey via email. For their time, participants will receive a \$10 Amazon gift code within 2 business days via email.

Confidentiality

Confidentiality will be maintained by all study staff along with the use of a secure study database.

All lab personnel and study staff will complete HIPAA and CITI trainings, human subjects protection training, responsible conduct of research training, and good clinical practices training. Phone scripts will be developed to ensure the subject is in an isolated environment where they are comfortable sharing personal information during the phone screen. During the study visit, participants will be taken to a private lab environment.

The secure databasing platform, REDCap, will store participant data. A subject ID will be assigned to each participant in order to deidentify study data. Multiple levels of security clearance are required before entering the REDCap system and only approved study personnel will have access to this data.

Compliance Statement

Research will be conducted in accordance with CTR policies and IRB regulations. Questions will be directed to OSU IRB representatives and S/AEs will be reported per IRB policy.

Statistical Considerations

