Data will be summarized descriptively. For hypothesis testing, we will use linear or logistic mixed effects regression models (with a random subject effect) to assess the main effects of product on plasma nicotine delivery, subjective effects, and behavioral intentions. Model assumptions will be checked, and variables will be transformed as needed. Missing data will not be imputed as likelihood-based linear mixed models will yield valid inference under missing at random assumptions. Models will control for age, sex, and other tobacco use if these features are not balanced by randomization. The same analysis strategy will be used for both aims. We calculated power for Aim 1 based on a repeated measures ANOVA comparing mean total nicotine delivery and maximum plasma nicotine concentration across 3 conditions; existing literature on differences in nicotine delivery across SLT products, including NPs, facilitates the use of this outcome for a power analysis.⁹ With a total sample size of only 20 participants and a Bonferroni-adjusted alpha of 0.017, we would have 84% power to detect a mean difference in total nicotine delivery of 25.7 ng/mL and 99% power to detect a mean difference of maximum nicotine concentration of 7.0 ng/mL between products.⁹ To account for attrition and the potential need for a larger sample size to detect differences in more subjective outcomes, we will recruit a

sample of 40 participants. For Aim 2, there are no known data to estimate effect sizes and thus to conduct power analyses. The sample size of 15 participants is intended to provide these data for future research.

5. Safety Management, Risks, and Benefits

Safety Management

Clinical Adverse Events

Clinical AE will be assessed by study staff at each study visit via participant self-report and managed immediately. Clinical AE may be related to nicotine overdose or the blood draw. Signs of nicotine overdose include nausea, vomiting, headache, presyncope, tachycardia, and disrupted sleep. With the blood draw, there is a slight risk of bruising, discomfort, and infection with blood draw. Study staff will be trained to recognize these signs and subjects will be encouraged throughout the visit to self-report any AE. In the event of a medical emergency, study staff will be advised to call 911 on the subject's behalf.

AE Reporting

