While this trial is not without risk, every effort will be taken to reduce risk and undue burden on participants.

Efforts to reduce risk are as follows:

1. Risk of using NP: The risk of side effects and adverse events are very low. Whether using tobacco-derived or synthetic nicotine, these products are sold online, and at specialty stores and convenience stores nationwide, without a prescription. Nevertheless, all participants will be screened for general medical precautions (pregnancy, cardiovascular disease) and monitored for adverse events during the study period. Study personnel will assess for adverse events via self-report at all follow-up visits. Subjects will also be provided a study phone line to report an adverse event between follow-up visits. Any serious adverse events will be reported to the PI and then to the OSU IRB and potentially to the NIH. We will withdraw participants who have a serious adverse event, or become pregnant or begin to breastfeed. The most likely adverse (potential for nicotine overdose) event is anticipated to be rare (<5% in our previous studies) and mild (nausea, headache, disrupted sleep) event will be handled quickly (i.e., advice to participant to reduce or stop NP use). Our on-site research nurse will also be available to escalate issues as needed and to handle any questions regarding reported adverse events. Lab studies of toxin exposure suggest that NPs incur no greater risk to health than do conventional cigarettes. Moreover, these are all over the counter products and are not significantly different from what the participant typically uses.

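### The $50 payment for an unfinished visit has no exception for adverse events, so a participant whose reported symptoms cut a visit short may lose part of the visit fee

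*Combined protocol and SAP*

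**What the plan says.** Under Payment to Subjects (Section 4), the visit fees are "Aim 1: For each clinic visit, subjects will receive \$150" and "Aim 2: For each clinic visit, subjects will receive \$100". Both aims carry the same bonus: "If participants complete all three visits within a month, they will receive a" $50 bonus. The stated maxima are "Participants could earn up to \$500 for their participation" (Aim 1) and "Participants could earn up to \$350 for their participation" (Aim 2). After the Aim 2 paragraph, and before the paragraph labelled for both aims, comes the rule at issue: "If any part of the visit is not possible to complete, participants will be given" $50. It names no cause and no exception.

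On detection, Clinical Adverse Events (Section 5) says: "Clinical AE will be assessed by study staff at each study visit via participant self-report and managed immediately". The same paragraph adds that staff learn to spot signs of nicotine overdose and that participants are urged to report. Clinic Visits (Section 2) has participants assessed for adverse events during the procedures and again before they leave. The Risk-Benefit Assessment (Section 5, item 1) repeats self-report as the method and adds a telephone line between visits and an on-site nurse. On the most likely symptoms it says: "event will be handled quickly (i.e., advice to participant to reduce or stop NP use". Administer intervention (Section 3) sets pouch use at 30 minutes.

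**The concern.** The plan asks participants to disclose symptoms during supervised nicotine use after 12 hours of abstinence. Several of the listed signs, such as nausea and headache, may be known only if the participant mentions them. The payment rule treats a visit that ends early for such symptoms like one that ends early for any other reason. A participant who feels unwell part-way through pouch use, and who knows the rule, has a financial reason to say nothing and finish. What is at stake is participant safety and full reporting of adverse events. The rule works against the encouragement to report that the plan gives elsewhere.

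**Working it through.** **Inputs**, all from Payment to Subjects: visit fee $150 (Aim 1) or $100 (Aim 2); bonus $50; payment for an unfinished visit $50.

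**Step 1: reproduce the plan's maxima.** Three visit fees plus the bonus.
- Aim 1: 3 × 150 + 50 = $500, as stated.
- Aim 2: 3 × 100 + 50 = $350, as stated.

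**Step 2: does the $50 replace the fee or add to it?** The text does not say. If it were added, an unfinished visit would pay 150 + 50 = $200 in Aim 1 and 100 + 50 = $150 in Aim 2, more than a finished one. Replacement is the only plausible reading.

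**Step 3: loss from one visit cut short.** Loss = visit fee − 50, plus 50 if the bonus is also lost.

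| | Aim 1 (if the rule applies there) | Aim 2 |
|---|---|---|
| Loss, bonus kept | 150 − 50 = $100 (67% of the fee, 20% of $500) | 100 − 50 = $50 (50% of the fee, 14% of $350) |
| Total received, bonus kept | $400 | $300 |
| Loss, bonus also lost | 100 + 50 = $150 (30% of $500) | 50 + 50 = $100 (29% of $350) |
| Total received, bonus lost | $350 | $250 |

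The text does not say whether a visit cut short counts as completed for the bonus, so both rows are shown.

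**Step 4: can a reported symptom trigger the rule?** The response to symptoms can include stopping the pouch. Pouch use is a 30-minute part of the visit, and the rule is triggered by any part left undone. Taken literally, early removal is enough. Clinic Visits also says that a missed blood draw is not taken later, so an interrupted schedule cannot be restored. The plan does not say whether early removal or a missed draw alone is meant to reduce payment.

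**Step 5: a related inconsistency.** Schedule return visit and provide gift card for participation (Section 3) gives $100 per visit and up to $350 without naming an aim (100 + 100 + 150 = 350). That matches Aim 2 only. If it governed Aim 1 too, the Aim 1 loss would be $50, or $100 with the bonus. The two sections need reconciling, but the point does not depend on which figure prevails.

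**Step 6: cost of paying safety-stopped visits in full.** Visits: 40 × 3 = 120 in Aim 1 and 15 × 3 = 45 in Aim 2, total 165. The Risk-Benefit Assessment puts the most likely event below 5% in earlier studies, without saying whether that is per participant or per visit. Assume 5% of visits, every one of them stopped: 6 in Aim 1 and 2.25 in Aim 2.
- Fees restored: 6 × 100 + 2.25 × 50 = $712.50.
- Fees and a bonus each time: 6 × 150 + 2.25 × 100 = $1,125.

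The Study Outline gives 20 rather than 15 participants for Aim 2. With 20 there would be 60 Aim 2 visits and 3 affected: 6 × 100 + 3 × 50 = $750, or 6 × 150 + 3 × 100 = $1,200.

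**The case against.** The strongest reply is that the chain from reporting to lost pay is inferred. No passage says that a reported symptom ends a visit. Stopping a pouch is not the same as stopping the visit, since draws and questionnaires can continue to 90 minutes, and the plan tolerates missed draws. The rule fits a failed abstinence check or a failed line placement at least as well, and the $50 is presented as thanks for time given. This stands in part: reporting a symptom that leaves the visit complete costs nothing. The rule's wording is nevertheless broad enough to reach a safety stop, and nothing visible excludes one.

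A reader might infer that detection rests only on what participants volunteer. The documents do not support that. Staff assess adverse events throughout the visit, are taught the signs, have a nurse on site, and meet the participant at each draw. Some signs, such as vomiting, are visible. Self-report is still the named method. The visit procedures schedule no heart-rate or blood-pressure reading although tachycardia is a listed sign, and the Study Outline mentions physiological data without specifying any.

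A reader might also infer that under-reporting would make the products look more alike on tolerability. No study objective and no outcome in Statistical Considerations is a tolerability comparison, and nothing shows that reporting would differ by product.

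Finally, an exception may exist in the procedure manual, to which gift-card administration is referred, or in the consent form. Neither was available. That limits the point to the protocol text, where a sentence would still be useful.

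**Conclusion.** The point holds as a gap in the payment rule. In Aim 2 a visit cut short for symptoms may cost the participant $50 of a $100 fee. In Aim 1 it may cost $100 of $150, provided the sentence, placed after the Aim 2 paragraph, is meant for both aims. The larger figures, 30% of the Aim 1 maximum and 29% of the Aim 2 maximum, should not be quoted on their own. Both need the visit to be treated as incomplete and the bonus to be lost with it, and the Aim 1 figure also needs the rule to cover Aim 1. All figures assume that the $50 replaces the fee.

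The disincentive is foreseeable, but the documents do not show that anyone under-reports. It does not threaten the nicotine-delivery, subjective-effect or intention comparisons on anything stated in the plan. The priority is optional to moderate.

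**What to change.** Amend the $50 sentence under Payment to Subjects along these lines: *A visit stopped or shortened because of an adverse event, or by a staff decision on safety grounds, is paid at the full visit fee and counts as completed for the bonus. A visit left incomplete for any other reason is paid $50. This applies to Aims 1 and 2.* State whether a missed draw alone counts as incomplete. Make sure participants are told, in the consent form if it is not already there and at the start of each visit. Reconcile the amounts in the return-visit section at the same time.

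This changes payment only, not clinical management. The cost is about $700 to $1,125 on the 5% assumption with 15 Aim 2 participants. It is probably less in practice, because that count treats every event as a stopped visit and includes the 40 Aim 1 cigarette visits, whereas the rate is quoted for pouch use. The other downside is a small risk that symptoms which cannot be verified are claimed in order to leave a visit of about three hours early. That would cost some blood samples, which matters more with 15 participants than with 40.
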